#### 3.3 Endpoints

#### 3.3.1 Primary Safety Endpoints

Long term safety performance will be evaluated by comparing the linearized rates listed below to the objective performance criteria referenced in ISO 5840-2005, Cardiovascular Implants-Cardiac Valve Prostheses

- Thromboembolism
- All Hemorrhage
- All Perivalvular Leak
- Endocarditis

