## 9.1 Sample Size Calculation

The sample size calculation for the trial is based on the primary safety endpoints. The linearized rates for thromboembolism, all hemorrhage, all perivalvular leak, and endocarditis will be compared to the Objective Performance Criteria from Annex R, Table R.1 per ISO 5840 as proposed by the US FDA in the Heart Valve Guidance draft 2009. These OPC are presented in Table 11.

Adverse Event	OPC
Thromboembolism	2.5
All Hemorrhage	1.4
All Perivalvular Leak	1.2
Endocarditis	1.2

Table 11: Safety OPC

More specifically, a statistical test based on the Poisson distribution will be performed for each of these adverse event rates to evaluate whether it is less than 2 times the appropriate OPC. Thus, the null and alternative hypotheses for each adverse event are as follows:

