## $H_0: \lambda \geq 2 \cdot OPC$

## $H_A: \lambda < 2 \cdot OPC$

This document and the information contained herein is considered Proprietary and Confidential and may not be reproduced, used or disclosed without written permission from Edwards Lifesciences LLC.

where  $\lambda$  is the linearized rate for the given adverse event (thromboembolism, valve thrombosis, all hemorrhage, all perivalvular leak, and endocarditis) computed when the total subject years reaches 808 and *OPC* denotes the relevant OPC. The test statistic for each adverse event is of the form:

$$Z = (\lambda - 2 \cdot OPC) / \sqrt{\lambda} .$$

 $H_0$  is rejected in favor of  $H_A$  if Z is less than -1.645, the lower 5% percentile of the standard normal distribution. Grunkemeier, et al. have demonstrated that 800 subject life-years is adequate to test against the smallest OPC of 1.2% per subject year (excluding valve thrombosis, and stratification for major versus minor hemorrhage, and perivalvular leak) with Type I and Type II error controlled at the .05 and .20 levels, respectively.

The proposed subject enrollment is calculated to ensure that at least 101 subjects survive to 8 years post implant. These 8\*101 = 808 life years in addition to the life years from those subjects not surviving to 8 years will more than fulfill the 800 life-years required by Grunkemeier, et al..

Sample size calculation for primary effectiveness endpoint is based on a test of the hypothesis:

 $H_0: p \le 75\%$  $H_A: p > 75\%$ 

where *p* is the proportion of the subjects in NYHA Class I or Class II at 8 years post implant. The expected proportion of the alive subjects in NYHA class I or II at eight years is approximately 90%, based on 7 year follow up data for the Carpentier-Edwards PERIMOUNT 6900/6900P valve (this proportion is essentially constant across each annual visit). Based on this expected proportion, a sample size of 45 subjects provides 85% power to test the hypothesis that the true proportion is greater than 75% using an exact binomial test. Thus, the sample size of 101 subjects with NYHA data at 8 year post implant is more than adequate to provide sufficient power.

This document and the information contained herein is considered Proprietary and Confidential and may not be reproduced, used or disclosed without written permission from Edwards Lifesciences LLC.

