#### **Bleeding Event**

A *bleeding event* is any episode of major internal or external bleeding that causes death, hospitalization, or permanent

injury (eg, vision loss) or necessitates transfusion. Major bleeding unexpectedly associated with minor trauma should be reported as a *bleeding event*, but bleeding associated with major trauma or a major operation should not. *Bleeding events* are reported for all patients regardless of whether they are taking anticoagulants or antiplatelet drugs. Although total *bleeding events* must be reported, *bleeding events* can also be reported separately for those who are taking anticoagulants or antiplatelet agents and those who are not.

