#### **19.0 APPENDIX 8: ADVERSE EVENT DEFINITIONS**

	Primary Event Name	Subcategory	General Definition	Device or Procedure Relationship
Bleeding Events	A bleeding event transfusion. Majo a major operation they are taking a those who are ta	is any episode of or bleeding unexpo- n is considered se nticoagulants or a king anticoagulan	f major internal or external bleeding that causes death, hospitalization, or permanent inji ectedly associated with minor trauma should be reported as a bleeding event, but bleed econdary to those events and should not be reported. Bleeding events are reported for a intiplatelet drugs. Although total bleeding events must be reported, bleeding events can ts or antiplatelet agents and those who are not. Bleeding Events are further categorized	ury (eg, vision loss) or necessitates ing associated with major trauma or ill patients regardless of whether also be reported separately for d as below.
	Bleed-Hemorrh	age		ISO 14155-1, Section 3.1 Adverse Device Effect (ADE) any untoward or unintended response to a medical device. ISO 14155-1, 3.18: Serious Adverse Device Effect (SADE) Adverse device effect that has resulted in any of the consequences characteristic of a serious adverse event or that might have led to any of these consequences if suitable action had not been taken or intervention had not been made or if circumstances had been less opportune.
	Anticoagulant- related Bleed (hemorrhage)		Any episode of major internal or external bleeding related to the use of anticoagulation that causes death, hosptalization, or permanent injury (e.g., vision loss) or necessitates transfusion.	Not defined
		Bleeding Diatheses related to AC	Bleeding diathesis is an unusual susceptibility to bleeding mostly due to a coagulopathy.	
	Coagulopathy		Development of a new bleeding disorder (one that was not diagnosed prior to the index procedure), documented by laboratory studies.	Event is procedure related if it occurs within 30 days of the date of the index procedure.
		DIC	Systemic /widespread formation of thromboses in the microcirculation, mainly within the capillaries. Secondary complication of a wide variety of coagulation disorders which activate the intrinsic coagulation sequence.	Not defined

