Bleeding Events	Pericardial Tamponade		Fluid accumulation between the myocardium and pericardium of the heart creating hemodynamic compromise. Severity of the tamponade may dictate the degree of intervention (invasive or non-invasive, surgical or Pericardiocentesis). This should be documented by either: 1. Echo showing pericardial fluid and signs of tamponade such as right heart compromise. 2. Systemic hypotension due to pericardial fluid compromising cardiac function.	Not defined

-				
	Procedural Bleeding		Any abnormal blood loss that occurs during the index procedure, in the opinion of the investigator. The volume of blood loss during the procedure shall be recorded on the case report form.	Not defined
	Post- Procedural		Abnormal bleeding that is related to the index procedure in the opinion of the investigator, that occurs after the patient leaves the OR.	Not defined
	Other Bleed, specify		Other bleeding event that does NOT fit in one of the above categories.	Not defined
Cardiac Complications				
	Angina		Angina is due to an inadequate supply of oxygen to the heart muscle. Symptoms may include: chest pain, tight or heavy feeling in the chest, or discomfort which spreads from the chest to the arm, back, neck, jaw, or stomach, numbness or tingling in the shoulders, arms or wrists, shortness of breath, and nausea relieved by rest or nitroglycerine. Stable angina has no change in frequency or pattern for 6 weeks. Angina which increases in frequency, intensity, or duration, which occurs at rest, or which is new in onset is considered unstable angina. Event should be documented and confirmed by EKG test results.	
		Angina -stable	No change in frequency or pattern for 6 weeks.	Not defined
		Angina-unstable	Chest pain extending over a 6-hour period that does not respond to treatment.	Not defined
	Annular Dissection		Dissection of the valvular annulus extending into the aorta which may occur due to disease state (friable tissue) or may be due to mechanical trauma such as over sizing of balloon expandable product, insertion of prosthetic valve or other valvular accessory product placement. Annular dissection occurring within 30 days of the index procedure will be considered related.	Event is considered procedure related if it occurs within 30 days of the index procedure.

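### Appendix 8 excludes bleeding from a major operation yet lists index-operation bleeding as a bleeding event, so early hemorrhage results are undefined, and the primary rate is exposed if 9.1 counts early events

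*Combined protocol and SAP*

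**What the plan says.** **Exclusion.** The Bleeding Events header in Appendix 8 requires death, hospitalization, permanent injury or transfusion. It treats bleeding associated with major trauma or a major operation as "econdary to those events and should not be reported" (the start of the first word is lost where the table column is split in the text copy). The Appendix 1 guideline, which the header follows, reads cleanly: "but bleeding associated with major trauma or a major operation should not".

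**Inclusion.** The same block then lists Procedural Bleeding, "Any abnormal blood loss that occurs during the index procedure, in the opinion of the investigator", with the volume lost to be entered on the case report form. It also lists Post-Procedural bleeding: "Abnormal bleeding that is related to the index procedure in the opinion of the investigator, that occurs after the patient leaves the OR". Neither row has a severity threshold, and the second has no end date. The GI Bleed row sends the reader back to the header for reportability; these two rows do not.

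**Use in the analysis.** Section 3.3.1: "Long term safety performance will be evaluated by comparing the linearized rates listed below to the objective performance criteria". All hemorrhage is one of the four rates. Its criterion in Table 11 is "All Hemorrhage 1.4" (percent per year), and the test is to "evaluate whether it is less than 2 times the appropriate OPC". Section 9.1 has the rate "computed when the total subject years reaches 808" and gives no 30-day limit. Section 9.3.1 reports early events (within 30 days) as a percentage of subjects, limits linearized rates to later events, and counts both in the Kaplan-Meier analysis.

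**The concern.** The index procedure is naturally read as a major operation, so the two rows gather what the header leaves out. A site can follow either line in good faith, particularly as 7.1 asks for every adverse event. Nothing later settles the matter: no section says which Appendix 8 rows form All Hemorrhage, and the Bleed-Hemorrhage row has no definition.

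Surgical bleeding reflects the operation more than the valve, and both rows rest on investigator opinion, so coding may differ between sites. The 30-day percentage and the freedom-from-hemorrhage curve move directly with the coding. If early events also entered the 9.1 test, a handful of operative bleeds could decide a primary endpoint, because the allowed number of events is small.

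**Working it through.** **1. The plan's own figure.** Section 9.1 cites 800 life-years for the smallest criterion, 1.2% per year, with one-sided alpha 0.05 and power 0.80. I used an exact Poisson test of H0: rate = 2 × 1.2%, with a true rate of 1.2%. Power first reaches 80% at 811 years (limit 12 events, power 0.816), within 3% of 800. At exactly 800 years the limit is 11 events and power is 0.741, because power moves in steps. The cited figure is reproduced.

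**2. Limit for all hemorrhage at 808 years.** The null mean is 0.028 × 808 = 22.62 events.
- Exact test: P(X ≤ 14) = 0.037 and P(X ≤ 15) = 0.060, so the limit is 14.
- Plan's Z applied to counts: (16 − 22.62)/√16 = −1.656 rejects; (17 − 22.62)/√17 = −1.364 does not. The limit is 16, with true alpha 0.094.

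**3. Late events expected at 808 years**, from the predecessor tables in Appendix 4 (7300TFX instructions, Tables 1 and 2).
- 6900P: 13/856.24 × 808 = 12.27
- 6900: 9/1072.5 × 808 = 6.78

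**4. Late-only reading (9.3.1).** Intra-operative bleeding falls on day 0 and adds no events to the primary count, whichever line is followed. Post-procedural bleeding adds events only if it occurs after day 30.

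**5. All-events reading (9.1 without a 30-day limit).** Mean = late events + 250 × share coded. P(pass) is the Poisson probability of not exceeding the limit. The share is an assumption.

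| Share coded | Events added | 6900P, exact (≤14) | 6900P, plan's Z (≤16) | 6900, exact (≤14) |
|---|---|---|---|---|
| 0% | 0 | 75% | 88% | 99.6% |
| 1% | 2.5 | 49% | 69% | 95% |
| 2% | 5 | 26% | 44% | 79% |
| 5% | 12.5 | 1.4% | 4% | 14% |

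**6. The documents' early bleeding percentages as the share**, exact limit.
- 6900P: 5/209 × 250 = 5.98 events added, mean 18.25, P(pass) 19%.
- 6900: 2/363 × 250 = 1.38 events added, mean 8.16, P(pass) 98%.

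The documents do not say whether these early counts include operative bleeding. The 6900 row is labelled anticoagulant-related hemorrhage in Appendix 4 and bleeding event in Appendix 9.

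**The case against.** A reader might infer that the primary all-hemorrhage result already turns on which line a site follows. The documents do not support that. Section 9.3.1 is headed as the primary safety endpoint and counts linearized events only after the early period, so operative blood loss stays out under either line. The predecessor tables use the same split. This stands, and it limits the claim.

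It does not close the question. The late-only sentences are introduced as being for reporting purposes and come after the paragraph on the hypothesis test. Section 9.1 defines the tested rate on total subject-years with no such limit. The Post-Procedural row can also produce an event after day 30. Section 9.2 does not help either way: it says which subjects and data are included and defines no numerator.

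Three further points have some force.
- A row in the bleeding block need not belong to All Hemorrhage. Hemolysis sits in that block and is a separate endpoint, and the header's severity criteria could be read as governing every row. But no section says so.
- All adverse events must be reported, the adverse event form records intra-operative onset and procedure causality, and the Clinical Events Committee reviews all reported events. Coded bleeds can therefore be found. However, the committee's stated adjudication task is relatedness, and it cannot see an event that a site leaves out under the header.
- The size depends on the predecessor chosen, the share assumed and the form of the test, as the table shows.

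**Conclusion.** The contradiction in Appendix 8 is real. Under any reading of the analysis sections it leaves the 30-day hemorrhage percentage and Kaplan-Meier freedom from hemorrhage dependent on which line is followed.

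The effect on the primary test is conditional. It is zero for day-0 bleeding if the tested rate is late-only. If 9.1 counts early events, an assumed 2% of 250 subjects with a coded bleed lowers the chance of passing at 808 years as follows:
- from 75% to 26% at the 6900P late rate with the exact limit;
- from 88% to 44% at the same rate with the plan's Z applied to counts;
- from 99.6% to 79% at the 6900 late rate with the exact limit.

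These figures assume that a major operation includes the index valve replacement, that all 250 subjects have been implanted when 808 years are reached, that events follow a Poisson distribution, and that predecessor late rates carry over. The documents give no frequency for index-operation bleeding as defined in the two rows.

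**What to change.** - **Appendix 8:** in the Procedural and Post-Procedural rows, state that bleeding from the index operation is recorded as an adverse event and tabulated separately, but is not counted in All or Major Hemorrhage. This agrees with the header and Appendix 1. List the rows that form All Hemorrhage.
- **Section 9.1:** state that the tested linearized rate counts events after 30 days, as 9.3.1 does.
- **Data:** recode early bleeding forms already collected on this rule before the test is run. Section 4.2 reports 249 subjects with a study valve in place at discharge by November 2013, so most such forms already exist.
- **Sensitivity:** add one analysis that counts index-operation bleeds.

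The cost is a few lines of text, the recoding and one extra table.

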#### 8.2.2 Clinical Events Review Committee

A Clinical Events Committee (CEC) will be responsible for the ongoing review of all reported adverse events and will serve to adjudicate the relationship of the event and the study device or surgical procedure. The CEC will be composed of independent physicians familiar with the treatment of valvular heart disease and cardiac surgery and a statistician will evaluate the rates of complications, including deaths and explants for all subjects in the study as well as the hemodynamic performance of the Magna Mitral valve. The CEC will be tasked with identifying any issues such as higher than expected complication and/or death rates or unanticipated adverse events or hemodynamic performance that is substantially better or worse than expected, to determine if the study should be stopped or changed at any time.

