## Definitions of Morbidity

## **Structural Valve Deterioration**

*Structural valve deterioration* includes dysfunction or deterioration involving the operated valve (exclusive of infection or thrombosis), as determined by reoperation, autopsy, or clinical investigation. Clinical investigation should include periodic echo-cardiographic surveillance. Substantially increased regurgitation or stenosis of the

From The American Association for Thoracic Surgery, a The Society of Thoracic Surgeons, b and the European Association for Cardio-Thoracic Surgery.c

This article is being published concurrently in *The Annals of Thoracic Surgery* and the *European Journal of Cardio-Thoracic Surgery*.

Received for publication Dec 11, 2007; accepted for publication Dec 11, 2007.

Address for reprints: [name], Cardiac Surgery, Cox 648, Massachusetts General Hospital, [name] (E-mail: [contact]).

J Thorac Cardiovasc Surg 2008;135:732-8

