#### Nonstructural Dysfunction

Nonstructural dysfunction is any abnormality not intrinsic to the valve itself that results in stenosis or regurgitation of the operated valve or hemolysis. The term nonstructural dysfunction refers to problems (exclusive of thrombosis and infection) that do not directly involve valve components yet result in dysfunction of an operated valve, as diagnosed by reoperation, autopsy, or clinical investigation. Examples of nonstructural dysfunction include the following: entrapment by pannus, tissue, or suture; paravalvular leak; inappropriate sizing or positioning; residual leak or obstruction after valve implantation or repair; and clinically important intravascular hemolytic anemia. In addition, nonstructural dysfunction includes development of aortic or pulmonic regurgitation as a result of technical errors, dilatation of the sinotubular junction, or dilatation of the valve annulus after either valve replacement with stentless prostheses (eg, pulmonary autograft, aortic allograft, and xenograft valves) or aortic valve-sparing operations if the cusps are seen to be normal at reoperation, autopsy, or clinical investigation. For percutaneous and transapical approaches to aortic valve replacement or conventional open aortic valve replacement, new onset of coronary ischemia from coronary ostial obstruction or paravalvular aortic regurgitation is considered nonstructural dysfunction. More than mild recurrent or residual mitral or tricuspid regurgitation after surgical or percutaneous interventional valve procedures (coronary sinus interventions, direct reparative methods, or other methods aimed at achieving ventricular remodeling) is nonstructural dysfunction, unless there is disruption of the valve components themselves, which would then be structural deterioration.

Sudden or progressive dysfunction or deterioration of the operated valve may be structural, nonstructural, or both, as determined by reoperation, autopsy, or clinical investigation.

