valvular		WIIG	than 25% of LVOT. Doppler Vena Contracta Width (cm) $< 0.3$ . Quantitative (by Echo	
			or Angio):Regurgitant volume (ml/beat) <30; Regurgitant fraction (%) <30;Regurgitant	
			orifice area (cm2) < 0.10.	
		Moderate	Qualitative: Angiographic grade- 2+; Color Doppler jet Width- Central jet, greater than	
			Mild but no signs of Sever AR. Doppler Vena Contracta Width (cm) 0.3-0.6.	
			Quantitative (by Echo or Angio):Regurgitant volume (ml/beat) 30-59; Regurgitant	
			fraction (%) 30-49;Regurgitant orifice area (cm2) 0.10-0.29.	
		Severe	Qualitative: Angiographic grade- 3-4+; Color Doppler jet Width- Central jet, width >	
			65% of LVOT. Doppler Vena Contracta Width (cm) >0.6. Quantitative (by Echo or	
			Angio):Regurgitant volume (ml/beat) >60; Regurgitant fraction (%) >50; Regurgitant	
			orifice area (cm2) >0.3.	
	Mitral Stenosis		Mitral stenosis (MS) refers to narrowing of the mitral valve orifice, resulting in	
			impedance of filling of the left ventricle in diastole. It is usually caused by rheumatic	
			heart disease. Less common causes include severe calcification of the mitral annulus,	
			intective endocarditis, systemic lupus erythematosus, rheumatoid arthritis, and experimed beart disease. The severity of MS is defined by the mitral value area $(M)(A)$	
			where normal valve area is 4 to 5 cm 	
		Mild	Mean gradient (mm Hg) < 5; Pulmonary artery systolic Pressure (mm Hg)< 30; Valve Area (cm2) >1.5.	
		Moderate	Mean gradient (mm Hg) 5-10; Pulmonary artery systolic Pressure (mm Hg) 30-50; Valve Area (cm2) 1.0-1.5.	
		Severe	Mean gradient (mm Hg) > 10; Pulmonary artery systolic Pressure (mm Hg)> 50; Valve Area (cm2)<1.0.	
	Mitral		Also known as mitral incompetence and mitral insufficiency is leakage of blood	
	Regurgitation		backward through the mitral valve each time the left ventricle contracts. Diagnosed by	
			auscultation (murmur) or echocardiography.	

	Mild	Qualitative: angiographic grade 1+; Color Doppler jet area- Small, central jet (<4 cm2 or<20% LA area); Doppler vena contracta width (cm) < 0.3. Quantitative (cath or echo):Regurgitant volume (ml/beat) <30;Regurgitant fraction (%) <30; Regurgitant orifice area (cm2) <0.20.	

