	Moderate	Qualitative: angiographic grade 2+; Color Doppler jet area- signs of MR greater than Mild present but no criteria for Sever Mr; Doppler vena contracta width (cm) 0.3-69. Quantitative (cath or echo):Regurgitant volume (ml/beat) 30-59;Regurgitant fraction (%) 30-49; Regurgitant orifice area (cm2) 0.20-0.39.	
	Severe	Qualitative: angiographic grade3-4+; Color Doppler jet area- Vena contracta width > 0.7 with large central MR jet (area > 40% of LA area) or with a wall-impinging jetof any size, swirling in LA; Doppler Vena contracta width > 0.7. Quantitative (cath or echo):Regurgitant volume (ml/beat) >/=60;Regurgitant fraction (%) >/=50; Regurgitant orifice area (cm2) >/=0.40.	
Tricuspid Stenosis		A narrowing of the tricuspid valve opening that increases resistance to blood flow from the right atrium to the right ventricle. Severe tricuspid stenosis is defined as a valve area less than 1.0 cm2.	
Tricuspid Regurgitation		Insufficiency of the tricuspid valve causing blood flow from the right ventricle to the right atrium during systole. Severe regurgitation characterized by Vena contracta width greater than 0.7 cm and Systolic flow reversal in hepatic veins.	
Other Valve, specify location:		Other valve (e.g. pulmonic) valve disease or deterioration reported after the AVR procedure.	
Structural Deterioration		Includes dysfunction or deterioration involving the replacement heart valve (exclusive of infection or thrombosis) determined by reoperation, autopsy or clinical investigation. Refers to changes intrinsic to the valve such as wear, fracture, leaflet escape, calcification, leaflet tear, stent creep, suture line disruption of components of prosthetic valve, new chordal rupture, leaflet disruption, or leaflet retraction of repaired valve.	By definition all are valve related .
	Calcification		
	Leaflet tear		
	Stress Fracture		
	Stent creep		
	Suture line disruption		
	vvear damage		
	Loss of structural integrity	Loss of structural integrity of metallic valve component such as wireform, frame, etc.	

		Other Structural		
		Deterioration,		
		specify:		
Valvular	Non Structural		Any abnormality not intrinsic to the valve itself that results in stenosis or regurgitation	
Valvalai	Dysfunction		of the replacement heart valve. Refers to problems (exclusive of thrombosis and	
	Dyoranotion		infection) that do not directly involve valve components yet result in dysfunction as	

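### Appendix 8 allows post-implant study-valve dysfunction to be filed as Mitral Stenosis or Mitral Regurgitation, outside the dysfunction endpoints, so structural, non-structural and possibly perivalvular leak rates may be understated

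*Combined protocol and SAP*

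**What the plan says.** Appendix 8 (section 19.0) is the dictionary by which adverse events are named. Its Valvular block has two mitral entries:

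- The Mitral Stenosis entry begins "Mitral stenosis (MS) refers to narrowing of the mitral valve orifice, resulting in". It names rheumatic disease as the usual cause and gives a normal area of 4 to 5 cm², so this is native-valve text.
- The Mitral Regurgitation entry begins "Also known as mitral incompetence and mitral insufficiency is leakage of blood". It names auscultation or echo as the means of diagnosis and says nothing of a prosthesis, so this is generic text.

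The same block has two entries for the prosthesis. Structural Deterioration reads "Includes dysfunction or deterioration involving the replacement heart valve (exclusive of infection or thrombosis) determined by reoperation, autopsy or clinical investigation". Non Structural Dysfunction covers stenosis or regurgitation of the replacement valve from a cause not intrinsic to it, and has perivalvular leak as a subcategory.

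Section 6.1.2 has events assessed by the STS guideline (Appendix 1) but reported by section 7.0 and Appendix 8. Adverse Event Form 6 takes one event per form, named from the listing. Neither mitral name is a safety endpoint in 3.3.1 or 3.3.2. Section 9.4.3 counts structural deteriorations and non-structural dysfunctions. Under 8.2.2 the Clinical Events Committee (CEC) "will serve to adjudicate the relationship of the event and the study device or surgical procedure".

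Appendix 1 has no separate mitral names. Its structural entry has a sentence, beginning "Substantially increased regurgitation or stenosis of the", that asks for such change with time to be reported quantitatively or semiquantitatively. Its non-structural entry gives "residual leak or obstruction after valve implantation or repair" as an example.

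**The concern.** In this trial a postoperative stenosis or regurgitation of the mitral valve is a finding on the device under test. The dictionary nevertheless offers a second home for it, and that home feeds no dysfunction rate. The cases most exposed are those seen on echo, managed without reoperation, and named by what the echo report says. An 8-year bioprosthesis study exists largely to count such cases.

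The list appears to have been carried over from an aortic study, where the mitral valve is not the study valve. The Appendix 8 row for other valves refers to an AVR procedure, the minor perivalvular leak row is partly worded as AI (aortic insufficiency), and the pacemaker item on Form 6 refers to AVR. The AI wording touches a primary endpoint, since all perivalvular leak is tested in 9.3.1: a mitral paravalvular jet fits the minor-leak row poorly and the Mitral Regurgitation row well.

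An event filed only under a mitral name can lower these rates but cannot raise them, so any error favours the device.

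**Working it through.** The plan states no figure on this point, so there is none to reproduce. The check is a trace of one event, followed by the size of the effect.

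**Trace.** Take a symptomatic central regurgitation of the study valve found at a scheduled echo and not reoperated.

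- Named Structural Deterioration, it enters the 9.4.3 rate and the actuarial curve.
- Named Mitral Regurgitation, it enters neither, nor anything in 3.3.1 or 3.3.2.
- Nothing in Appendix 8, Form 6 or section 9 says which name takes precedence, and 8.2.2 does not state that the CEC may change a name.

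**Expected counts.** Study rates are unknown. As an assumption I use the predecessor valves (Appendix 9, Tables 3 and 4): model 6900 with 1,072.5 late patient-years and 6900P with 856.24. Rate = events / patient-years × 100. Expected count = events / patient-years × 808, the exposure named in section 9.1.

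| Late event | 6900: n, rate | Expected at 808 | 6900P: n, rate | Expected at 808 |
|---|---|---|---|---|
| Structural | 5, 0.47 | 3.8 | 2, 0.23 | 1.9 |
| Non-structural | 3, 0.28 | 2.3 | 1, 0.12 | 0.9 |
| Perivalvular leak | 5, 0.47 | 3.8 | 2, 0.23 | 1.9 |

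**Weight of one event.** 100 / 808 = 0.12 per 100 subject-years. Section 9.1 expects exposure above 808; at an assumed 1,300 subject-years it is 100 / 1,300 = 0.08.

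**Share miscoded.** The documents do not give it. Reported rate = true rate × (1 − share), at the 6900 rates:

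| Share | Structural | Non-structural |
|---|---|---|
| 0% | 0.47 | 0.28 |
| 10% | 0.42 | 0.25 |
| 25% | 0.35 | 0.21 |
| 50% | 0.23 | 0.14 |

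**Primary leak test.** The limit is 2 × 1.2 = 2.4 per 100 subject-years, or 808 × 0.024 = 19.39 events. I read the printed statistic on event counts, Z = (N − 19.39)/√N. Then N = 13 gives −1.77 and N = 14 gives −1.44, so against −1.645 the test passes at 13 or fewer. Predecessor rates imply 1.9 to 3.8 leaks. Diverted leaks would change the reported rate, but would change the test result only if the true count were 14 or more.

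**The case against.** The strongest reply is that the right codes already exist. The structural and non-structural rows name the replacement valve and accept clinical investigation as evidence, the structural row has an open category for other deterioration, and section 6.1.2 sends the assessor to Appendix 1. The general perivalvular leak definition is not specific to the aortic position, and AI is only one of the two minor-leak criteria. The mitral names also have a legitimate use, because Form 6 allows preoperative onset and subjects are enrolled at consent. The core lab grades mitral regurgitation independently, and its severity is a secondary effectiveness endpoint (9.5.2). All of this stands, and it is why the conclusion is "may" in substance rather than a demonstrated bias. It does not close the gap: the reported name drives the count, and a cross-sectional severity table is not an event rate.

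Three stronger readings are tempting, and the documents support none of them.

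- A reader might infer that such events reach no safety endpoint at all. Those leading to reoperation, explant or death are counted under those headings whatever the underlying name. Valve-related death is less secure, because Appendix 1 defines it by listed causes that include neither mitral name.
- A reader might set echo prevalence against event counts. In model 6900, 12 of 131 subjects (9.2%) had 2+ or worse regurgitation at 1 to 2 years, against 5 + 3 = 8 late structural and non-structural events. In 6900P it was 6 of 160 graded at 1 year (3.8%), against 2 + 1 = 3. These are findings at one visit. Nothing shows that any was an adverse event, worsened, or was filed under another name.
- A reader might take the empty relationship cells in the two mitral rows, or the vena contracta range printed as 0.3-69, as further proof. Other prosthesis rows have empty cells too, Form 6 records causality for every event, and the range looks like a misprint.

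**Conclusion.** The point holds as a classification fault with a possible one-sided bias. For this trial the dictionary contains two names that overlap the endpoint codes for the study valve, and no rule separates them. Structural deterioration and non-structural dysfunction rates may be understated, and perivalvular leak possibly so. That they are understated is not shown: with no miscoding there is no bias.

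The size rests on two assumptions, predecessor event rates and 808 subject-years. With so few events expected, one or two diverted cases would visibly change a reported rate. The structural and non-structural rates are descriptive secondary endpoints without a performance criterion, so no hypothesis test depends on them. The leak test is exposed in principle but is unlikely to change at predecessor rates. The matter should be corrected because durability is the study's purpose and the remedy is cheap.

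**What to change.** 1. In Appendix 8, restrict Mitral Stenosis and Mitral Regurgitation to preoperative disease, or remove them.
2. State that any post-implant stenosis or regurgitation adverse event of the study valve is classified under the existing codes: structural deterioration, non-structural dysfunction (including perivalvular leak), valve thrombosis or endocarditis. Use Appendix 1's wording. Have the CEC confirm the code, informed by the jet location that the core lab already records (paravalvular, central or indeterminate; Appendix 3, section 4.4.8). Add this task to 8.2.2.
3. Set no automatic default to structural deterioration. Appendix 1 speaks of substantial increase over time, and sending every central jet above mild to that code could inflate the rate.
4. In the minor perivalvular leak row, replace AI with regurgitation of the study valve.
5. Before analysis, recode events already filed under the two names, and report how many moved and to which code.

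The cost is a wording change, a modest addition to CEC work and limited recoding; the documents do not say how many events are affected. The reported dysfunction rates may become slightly less favourable.
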